4.2.2.2. Intercurrent Events and Missing Data

Intercurrent events during the on-treatment phase of the study can result in missed on-treatment visits and participant data not being collected. This missing data can potentially confound the interpretation of the primary endpoint. The intercurrent event of use of rescue medication has been incorporated into the definition of the variable (composite strategy). The intercurrent event of discontinuation of, interruption of, and adherence to investigational product (IP) unrelated to wide disruptive events (WDEs) will be analysed as collected (treatment policy).

Missing Primary Data On-Treatment, End of Treatment (EOT) and Off-Treatment

For participants where WDEs on-treatment result in discontinuation of, significant interruption of, and adherence to investigational product (IP), and the participant returns to the study and has data in the on-treatment period, the data will be handled in the following two ways:

1. For observed VR responders, the data will be analysed as collected (treatment policy). No imputation of missing data will be performed.
2. For observed VR non-responders, data collected after the intercurrent event will be set to missing. Their SVR response will be imputed assuming missing at random using all available data from participants for whom SVR can be assessed (hypothetical strategy).

Significant interruption/non-adherence is defined as a gap of ≥ 21 days between treatment doses at any time during the on-treatment period (excluding the PegIFN Eligibility Period). The final inference from the Bayesian model will account for the missing data assuming MAR. End of treatment (EoT) VR response will be determined using the end of treatment analysis windows defined in [Table 2](#), [Table 3](#), and [Table 4](#). In the absence of rescue medication usage, if all HBsAg and HBV DNA data within the analysis window for the EoT visit is missing and the missingness is not due to wide disruptive events, the subject will be considered as an SVR non-responder. No imputation of missing data will be performed.

If all HBsAg and HBV DNA data within the analysis window for the EOT visit is missing due to a WDE, and the participant withdraws from the study due to the WDE, the participant will be classified as not reaching EOT at follow-up. Data after the intercurrent event will be set to missing, and their SVR response will be imputed assuming missing at random using all available data from participants for whom SVR can be assessed.

If all HBsAg and HBV DNA data within the analysis window for the EOT visit is missing due to a WDE, but the participant later returns to study and has non-missing data in an analysis window, the data will be handled in the following two ways:

1. For observed VR responders, the data will be analysed as collected (treatment policy). No imputation of missing data will be performed.
2. For observed VR non-responders, data collected after the intercurrent event will be set to missing. Their SVR response will be imputed assuming missing at random using all available data from participants for whom SVR can be assessed (hypothetical strategy).

If all HBsAg and HBV DNA data within an analysis window after the planned end of sequential treatment (EoT) is missing unrelated to wide disruptive events, missing data will be considered as an SVR non-responder. No imputation of missing data will be performed.

If all HBsAg and HBV DNA data within an analysis window after the planned end of sequential treatment (EoT) is missing due to wide disruptive events, the participant's SVR status will be considering as missing due to WDE. Data after the intercurrent event will be set to missing, and the SVR response will be imputed using all available data from participants for whom SVR can be assessed.

If the participant has any HBsAg \geq LLOQ or HBV DNA \geq LLOQ or rescue medication usage at or after the planned end of sequential treatment (EoT), the subject will be classified as an SVR non-responder. No imputation of missing data will be performed.

If a participant has any assessments that are affected by a wide disruptive event, but the participant's HBsAg and HBV DNA within an analysis window are collected and the participant is a VR responder, the subject will be classified as an SVR responder.

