9.4.2.1. Main Estimands

Main Estimands supporting the primary objective are defined as:

- Population: Participants with CHB on stable NA therapy
- Treatment: 300 mg GSK3228836 for 12 or 24 weeks followed by up to 24 weeks of PegIFN therapy while on stable NA therapy
- Variable (Categorical): Participants achieving Sustained Virologic Response (HBsAg <LLOQ and HBV DNA <LLOQ) for 24 weeks after the planned end of sequential treatment, without use of any rescue medication
- Intercurrent Events:
 - Discontinuation of, interruption in, and non-adherence to GSK3228836 and PegIFN not related to any wide disruptive events (such as COVID-19 pandemic) will be ignored (treatment policy strategy).
 - Ineligibility to receive PegIFN will be ignored (treatment policy strategy)
 - Use of rescue medication (composite strategy).
 - Wide disruptive events (such as COVID-19 pandemic) leading to discontinuation of, interruption in, and non-adherence to GSK3228836 and PegIFN will be handled assuming they had not happened (hypothetical strategy).
- Population-level Summary: The percentage of participants in each treatment group who achieve Sustained Virologic Response (HBsAg <LLOQ and HBV DNA <LLOQ) for 24 weeks after the planned end of sequential treatment, without use of any rescue medication

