9.4.2.3. Handling of Withdrawal from Study and Missing HBsAg and HBV DNA Data

Two approaches will be used to determine a participant's response when HBsAg and HBV DNA data are missing from visits required to derive the primary Estimand.

1) For participants where wide disruptive events (such as COVID-19 pandemic) prevent assessment of the primary outcome, SVR will be imputed using all available data for participants for whom SVR can be assessed. For other participants where SVR in the absence of rescue medication cannot be ascertained due to missing data (withdrawal from the study or missing due to other reasons, but not due to a wide disruptive event), the participant will be assumed not to have achieved SVR (non-responder imputation).

2) For the main estimand supporting the primary objective, a sensitivity analysis will be performed using the Bayesian model described in Section 9.4.2.4 assuming missing at random whereby a participant's response will be imputed using all available data (on and off treatment values) for participants who completed the study.

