4.2.1. Definition of Estimands

The primary estimand supporting the primary objective is defined as:

- **Population:** Participants with CHB on stable NA therapy.
- **Treatment:** 300 mg GSK3228836 for 12 or 24 weeks followed by up to 24 weeks of PegIFN therapy while on stable NA therapy.
- **Variable (Categorical):** Participants achieving sustained virologic response (SVR) (HBsAg <LLOQ and HBV DNA <LLOQ) for 24 weeks after the planned end of sequential treatment, without the use of rescue medication.
- **Intercurrent Events:**
 - For discontinuation of, interruption in, or non-adherence to GSK3228836 or PegIFN unrelated to any wide disruptive events (such as COVID-19 pandemic), the data will be analysed as collected (treatment policy strategy).
 - For participants that are ineligible to receive PegIFN, the data will be analysed as collected (treatment policy strategy).
 - Use of rescue medication will be incorporated in the definition of the endpoint (composite strategy).
 - For wide disruptive events (such as COVID-19 pandemic) leading to discontinuation of, significant interruption in, or non-adherence to GSK3228836 and PegIFN, data collected after the intercurrent event will

be set to missing and the response will be imputed assuming missing at random in the Bayesian model. Additional details provided in Section 4.2.2.2 (hypothetical strategy).

- **Population Summary:** The percentage of participants in each treatment group who achieve sustained virologic response (SVR) (HBsAg <LLOQ and HBV DNA <LLOQ) for 24 weeks after the planned end of sequential treatment without rescue medication usage.

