The third supplementary estimand examines the effect of the intercurrent event of a participant failing to meet PegIFN eligibility criteria by PegIFN Eligibility Week 13 (i.e. can no longer receive at least 12 weeks of PegIFN treatment). The estimand strategy for this intercurrent event will be principal stratum, which restricts the population to participants for whom the intercurrent event did not occur. The third supplementary estimand is defined as:

- **Population:** Participants with CHB on stable NA therapy that have received at least 12 doses of PegIFN
- **Treatment:** 300 mg GSK3228836 for 12 or 24 weeks followed by up to 24 weeks of PegIFN therapy while on stable NA therapy.
- **Variable:** The percentage of participants that achieve SVR for 24 weeks after the planned end of sequential treatment without the use of rescue medication
- **Intercurrent Events:**
 - For discontinuation of, interruption in, or non-adherence to GSK3228836 or PegIFN unrelated to any wide disruptive events (such as COVID-19 pandemic), the data will be analysed as collected (treatment policy strategy).
 - For participants that are ineligible to receive PegIFN, the data will be analysed as collected (treatment policy strategy).
 - Use of rescue medication will be incorporated in the definition of the endpoint (composite strategy).
 - For wide disruptive events (such as COVID-19 pandemic) leading to discontinuation of, significant interruption in, or non-adherence to GSK3228836 and PegIFN, data collected after the intercurrent event will be set to missing and the response will be imputed assuming missing at random in the Bayesian model (hypothetical strategy).

- **Population Summary:** The percentage of participants in each treatment group who achieve SVR for 24 weeks after the planned end of sequential treatment without use of any rescue medication.

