 - For wide disruptive events (such as COVID-19 pandemic) leading to discontinuation of, significant interruption in, or non-adherence to GSK3228836 or PegIFN, data collected after the intercurrent event will be set to missing and the response will be imputed using all available data for participants for whom SVR can be assessed. (hypothetical strategy).

Population Summary: Difference in percentage of participants who achieve SVR for 24 weeks after the planned end of sequential treatment between treatment arms

Categorical Variables

The following categorical variables are defined for this objective:

- Achieving SVR (HBsAg <LLOQ and HBV DNA <LLOQ) at the planned end of sequential treatment and over the 24 weeks follow-up for each treatment arm.

Main Analytical Approach

The secondary efficacy comparison of interest is the difference in sustained virologic response rate for 24 weeks after the planned end of sequential treatment between treatment arms:

- Arm 1 vs. Arm 2 in percentage of participants achieving SVR for 24 weeks after the planned end of sequential treatment, without use of any rescue medication.

Comparison between treatment arms will be made by calculating the difference between the posterior distributions of the response rate in each arm which will be summarised to obtain posterior means and CIs. Samples from the posterior distribution of the response rates in each arm will also be used to obtain posterior probabilities of interest. The point estimates of differences in SVR rate with 95% credible intervals will be calculated for the treatment comparisons described in the estimands. Posterior probabilities $\Pr(\text{Arm 1} - \text{Arm 2} > 0)$ and $\Pr(\text{Arm 2} - \text{Arm 1} > -0.05)$ will be presented to aid selection of treatment regimen.

Model Checking and Diagnostics – MCMC Mixing Diagnosis

The same approach in model checking and diagnostics will be applied as for the primary analysis (Section 4.2.2.3).

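### After a wide disruptive event, SAP 4.2.2.2 keeps observed responders but erases and imputes observed non-responders, against the outcome-blind rule in SAP 4.2.1 and with no order of precedence

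*SAP*

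**What the plan says.** SAP 4.2.1 defines the primary estimand. Where a WDE leads to discontinuation, significant interruption or non-adherence, post-event data are removed and "the response will be imputed assuming missing at random in the Bayesian model. Additional details provided in Section 4.2.2.2 (hypothetical strategy"). It draws no distinction by what was observed. The same undivided rule appears in SAP 4.2.4.3 ("will be set to missing and the response will be imputed assuming missing at random in the Bayesian model (hypothetical strategy")) and SAP 4.3.1.3 ("data collected after the intercurrent event will be set to missing and the response will be imputed using all available data for participants"), neither of which points to 4.2.2.2. Protocol 9.4.2.1 has no split by outcome either: "non-adherence to GSK3228836 and PegIFN will be handled assuming they had not happened (hypothetical strategy"). Protocol 9.4.2.3 is narrower and imputes only where such events "prevent assessment of the primary outcome, SVR will be imputed using all available data for participants for whom SVR can be assessed".

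SAP 4.2.2.2 then divides the same kind of participant. Where a WDE caused discontinuation or a dosing gap of 21 days or more and "the participant returns to the study and has data in the on-treatment period", there are two branches:

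- Responders: "For observed VR responders, the data will be analysed as collected (treatment policy). No imputation of missing data will be performed".
- Non-responders: "For observed VR non-responders, data collected after the intercurrent event will be set to missing", and SVR is imputed under MAR.

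The split is repeated for participants who miss the end-of-treatment (EoT) window because of a WDE and later return, and again for the interim in SAP 4.7.4.1. Footnote 1 in SAP 4.2.2.1 does the same at assessment level, relabelling an observed non-response as missing due to a WDE.

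Two later sentences of 4.2.2.2 bear on the same people. One makes any HBsAg or HBV DNA value at or above LLOQ, or rescue use, at or after planned EoT a final SVR non-response without imputation. The other grants SVR to a WDE-affected participant who is a VR responder within an analysis window, in the singular; SAP 4.2.2.1, where all windows have data, requires response in each.

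**The concern.** An observed failure is removed because it is a failure, while an observed success under the same disruption is kept. Missingness then depends on the removed value, so MAR fails by construction, and the imputation draws on a data set from which failures have been selectively taken out. The estimand also becomes mixed: treatment policy for those who did well, hypothetical for those who did not.

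Separately, the section does not say which rule applies first. An affected participant who returns with a value at or above LLOQ at EoT is imputed under the split and is a fixed non-responder under the later sentence. That is an ambiguity in the primary endpoint itself. SAP 4.8 (Table 10), which lists departures from the protocol, does not mention the split.

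**Working it through.** **1. The plan's own figures.** SAP 5 uses n = 50 per arm, a Beta(0.5, 0.5) prior and a posterior probability above 65%. The minimum responder counts are 12 (threshold 20%) and 17 (threshold 30%). Binomial tails give 86.1% for threshold 20% at true 30%, 28.9% for threshold 20% at true 20%, 31.6% for threshold 30% at true 30%, and 84.4% for threshold 30% at true 40%. The SAP states 86%, 29%, 32% and 84%, so its table reproduces.

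**2. Shift per affected participant.** Let p be the true SVR rate, q the probability that a VR at EoT is sustained, and π = p/q the VR rate. Under the split, expected SVR is πq + (1−π)p; outcome-blind imputation gives p. The difference is π(q−p), upward whenever q exceeds p. At p = 0.30:

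- q = 0.5: 0.6 × 0.2 = 0.12, so 0.42 instead of 0.30
- q = 0.75: 0.4 × 0.45 = 0.18, so 0.48
- q = 1: 0.3 × 0.7 = 0.21, so 0.51

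**3. Shift in the arm estimate.** Let f be the share of the arm affected. The documents give neither f nor q, so f = 2%, 5%, 10% and q = 0.5 to 1 are assumptions. Erased non-responders contribute nothing under MAR, so the estimate is

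[(1−f)p + fπq] / [1 − f(1−π)] = p / [1 − f(1−p/q)].

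Example: f = 0.10, q = 0.5 gives 0.30 / 0.96 = 0.3125. For the criterion P(rate>30%)>65%, the erased count is Bin(50, f(1−p/q)) under the split and Bin(50, f) under the outcome-blind rule.

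| f | Estimate, split | Criterion met, split | Criterion met, outcome-blind |
|---|---|---|---|
| 2% | 30.2-30.4% | 35.3-37.4% | 35.5% |
| 5% | 30.6-31.1% | 39.0-42.3% | 35.9% |
| 10% | 31.3-32.3% | 43.2-48.8% | 35.1% |

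The outcome-blind estimate stays at 30%. Its criterion column lies above 31.6% only because the denominator varies and the binomial is discrete, so the fair comparison is across a row. At f = 2% (one participant in 50) the difference lies within that discreteness.

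**4. Sensitivity.** If disruption halves the VR rate of those affected, f = 10% gives 30.6-31.2% and 39.4-42.0%. If it cuts that rate to a quarter, the estimate is 30.3-30.6%; if to zero, there is no bias. With two equal strata at 50% and 10% and the split applied within stratum, the estimates are 30.1-30.3%, 30.2-30.9% and 30.4-31.8% at f = 2%, 5% and 10%.

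**5. One participant at the boundary.** 16 of 50 gives a posterior probability of 0.628 for a rate above 30%, which misses the criterion. Erase one affected non-responder and 16 of 49 gives 0.664, which meets it.

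**6. A half-fix reverses the bias.** If the split is removed but the LLOQ sentence still applies to affected participants, responders are imputed and failures kept. The estimate is (1−f)p / (1−fp): 29.6%, 28.9% and 27.8% at f = 2%, 5% and 10%.

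**The case against.** Several points on the other side have weight.

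- **Scope.** The split covers returners only. Those who miss EoT because of a WDE and withdraw, or whose post-EoT window is missing because of one, are imputed without a split. This is correct, and the point is limited accordingly.
- **Deferral.** SAP 4.2.1 refers to 4.2.2.2 for details, so a programmer would follow 4.2.2.2. But moving responders from hypothetical to treatment policy is a change of strategy rather than a detail, and 4.2.4.3 and 4.3.1.3 carry no such pointer.
- **Narrower reading.** The bias and the precedence gap are largely alternatives: if the LLOQ sentence governs, the bias shrinks toward zero. SAP 4.7.4.2 ties that condition to a post-EoT window missing because of a WDE, which may be the intended scope. SAP 4.2.2.2 does not say so, and on that reading the split governs.
- **Rationale.** Response despite interrupted treatment is informative, so keeping responders is defensible. That does not justify treating observed non-responders as if nothing had been seen.
- **Mitigation.** SAP 4.2.5.2 analyses restarters as collected. A gap between doses implies that dosing resumed, so it covers more of the interruption group than first appears. It omits those who stop for good but still supply data, and it is an additional estimand that leaves the primary result unchanged. The sensitivity analysis in SAP 4.2.3 assumes MAR for all missingness and states no rule restoring erased failures.
- **Choice of remedy.** Analysing every assessable participant as collected would also be outcome-blind and closer to Protocol 9.4.2.3. That is a fair alternative, but it would give up the hypothetical strategy that both documents declare for the main estimand.

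**Conclusion.** The concern holds and should be fixed. Among WDE-affected returners, SAP 4.2.2.2 deletes data according to outcome, contrary to the rule in SAP 4.2.1, 4.2.4.3 and 4.3.1.3, and it contains an unranked rule that classifies some of the same participants differently. The contradiction needs only one affected participant to matter.

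The bias is conditional and probably modest. If the split governs, it is upward whenever q exceeds p: about 0.6 to 1.1 percentage points at 5% affected and 1.3 to 2.3 at 10%, for a true SVR of 30%, assuming that disruption does not alter response and ignoring strata. It is smaller under stratification or a disruption-reduced VR rate, negligible at one participant per arm, and zero if nobody is affected. These are Beta-binomial planning calculations, whereas the primary model is a stratified logistic regression. The study is descriptive; the 65% criterion appears only in the planning tables, and the actual decision framework is in a charter outside these documents.

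**What to change.** - Apply one outcome-blind rule to every participant with a qualifying WDE. To match SAP 4.2.1 and 4.3.1.3, set post-event data to missing and impute SVR for responders and non-responders alike.
- Remove the split in both places in SAP 4.2.2.2 and in 4.7.4.1, and the relabelling in footnote 1 of 4.2.2.1.
- In the same revision, state that the sentence on values at or above LLOQ at or after EoT does not apply to data set to missing under this rule. Changing only one of the two would bias the estimate downward.
- In the closing sentence of 4.2.2.2, require response in each analysis window, and limit it to participants without a qualifying discontinuation or gap.
- List the rule in Table 10, because Protocol 9.4.2.3 imputes only where assessment was prevented.
- Extend the as-collected analysis in 4.2.5.2 from restarters to all affected participants, show it beside the primary result, and report the numbers affected and reclassified in each arm.

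The cost is SAP wording and derivation code, slightly wider intervals because affected responders are also imputed, and possibly a slightly lower reported SVR.

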The study team may enrol additional participants to within 10% of the planned 100.

Note: "Enrolled" means a participant's, or their legally acceptable representative's, agreement to participate in a clinical study following completion of the informed consent process and after study personnel have confirmed that all eligibility criteria have been met. Potential participants who are screened for the purpose of determining eligibility for the study, but do not participate in the study, are not considered enrolled, unless otherwise specified by the protocol.

Intervention Arms and Duration:

The total duration of the study, including screening, treatment, and post-treatment follow-up, is not expected to exceed 79 weeks for each participant:

- Arm 1: 24 weeks GSK3228836 + 24 weeks PegIFN + 24 weeks off-treatment
- Arm 2: 12 weeks GSK3228836 + 24 weeks PegIFN + 36 weeks off-treatment

[figure not shown]
A 45-day screening window is included in the total study duration. Eligible participants who fall outside of the 45-day window may be re-screened at the discretion of the Investigator/site.

There are no plans for group dose adjustments. Individual dose adjustments for GSK3228836 for safety are outlined in the monitoring/stopping criteria. Individual dose adjustments for PegIFN for safety are outlined in the monitoring/stopping criteria and are permitted down to 90 mcg/mL.

Participants that leave the study early will not be replaced.

Data Monitoring/ Other Committee: Yes

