4. STUDY DESIGN

4.1. Overall Design

This is a Phase IIb, multi-centre, randomised, open-label study to assess the efficacy and safety of sequential treatment with GSK3228836 (300 mg/week for 12 or 24 weeks) followed by PegIFN (180 mcg/week for up to 24 weeks) in participants with CHB on stable NA therapy. During the GSK3228836 treatment period, a 300 mg loading dose will be administered on Day 4 and Day 11. Participants will continue their NA therapy for the duration of the study.

Participants will be randomised (1:1) into one of two parallel treatment arms.

1. 300 mg GSK3228836 once/week for 24 weeks (plus loading dose on Day 4 and 11) followed by PegIFN (180 mcg/week for up to 24 weeks). Participants will be followed up for an additional 24 weeks (off-treatment phase) once PegIFN treatment is complete.

2. 300 mg GSK3228836 once/week for 12 weeks (plus loading dose on Day 4 and 11) followed by PegIFN (180 mcg/week for up to 24 weeks). Participants will be followed up for an additional 36 weeks (off-treatment phase) once PegIFN treatment is complete.

The planned duration of GSK3228836 is 24 weeks and 12 weeks in Treatment Arm 1 and 2 respectively. If a participant prematurely discontinues GSK3228836 treatment the participant is encouraged to complete the SoA as per the planned GSK3228836 dosing period. At the end of the planned GSK3228836 dosing period, participants will be re-assessed for eligibility to start PegIFN treatment based on the label.

1. Participants immediately eligible for PegIFN will begin treatment
2. Participants who are not considered eligible will be re-assessed for eligibility and may delay start of PegIFN treatment for up to 12 weeks.
3. Participants who fail to meet PegIFN eligibility criteria by PegIFN Eligibility Week 13 (i.e. can no longer receive at least 12 weeks of PegIFN treatment) will not receive treatment with PegIFN.

Note: all participants are expected to end PegIFN treatment at the same time, regardless of when they start therapy (Treatment Group 1: all participants should complete treatment by Week 48; Treatment Group 2: Week 36).

As such, the planned treatment duration with PegIFN for participants on study 209348 may vary from a minimum of 12 weeks to a maximum of 24 weeks.

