9.4.2. Primary Objective

The primary analysis for the primary objective will be conducted once the last participant has completed the Week 72 visit and database lock has achieved.

The primary efficacy endpoint is achieving a sustained virologic response for 24 weeks after the planned end of GSK3228836 and PegIFN sequential treatment in the absence of rescue medication. Sustained virologic response is defined as observing HBsAg <LLOQ and HBV DNA <LLOQ at each analysis window in the 24 weeks after the end of sequential treatment. Analysis windows for the post sequential treatment assessments will be defined in the analysis plan.

HBsAg and HBV DNA from the week of end-of-treatment to Off-Treatment Week 24 will be used to assess the primary endpoint for each arm.

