4.2. Primary Endpoint Analyses

HBsAg and HBV DNA assessments from the end of treatment analysis window (Week 48 or Week 36 for Arm 1 and Arm 2 respectively) to the off-treatment Week 24 analysis window will be used to analyse the primary endpoint for each arm. The primary analysis for the primary endpoint will be conducted once the database lock has been achieved and the last participant has completed the Week 72 visit.

The primary efficacy endpoint is achieving a sustained virologic response for 24 weeks after the planned end of GSK3228836 and PegIFN sequential treatment in the absence of rescue medication. Sustained virologic response (SVR) is defined as observing HBsAg <LLOQ and HBV DNA <LLOQ at each analysis window in the 24 weeks after the end of sequential treatment. Analysis windows for the post GSK3228836 treatment assessments are defined in Section 4.2.2.1.

An estimation approach with no hypothesis testing will be used to address the primary objective. The primary assessments of interest are the point estimate of SVR rate and 95% credible intervals. In addition, posterior probabilities that the true SVR rate in each treatment arm is greater than a range of clinically meaningful response rates will be provided. The point estimates for SVR will be calculated using a Bayesian probability approach. Comparisons between treatment arms as defined in the key secondary/exploratory objectives will be assessed using probability inference approaches.

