Analysis Set	Parameter	Target Study Day	Analysis Window		Analysis Timepoint	Protocol Visit
			Beginning Timepoint	Ending Timepoint		
Efficacy	HBsAg and HBV DNA	78	64	Minimum of (98, PegIFN First Dosing Study day)	End of GSK3228836 treatment	Week 12
Efficacy	HBsAg and HBV DNA	246	211	266	End of PegIFN Treatment / EoT	Week 36
Efficacy	HBsAg and HBV DNA	302	267	322	Post PegIFN treatment Week 8	Off-treatment Week 8
Efficacy	HBsAg and HBV DNA	372	323	378	Post PegIFN treatment Week 18	Off-treatment Week 18
Efficacy	HBsAg and HBV DNA	414	379	434	Post PegIFN treatment Week 24	Off-treatment Week 24

The primary analysis will be based on planned end of treatment regardless of whether a patient discontinued treatment.

For the first and second supplementary estimands described in Section 4.2.4.1 and Section 4.2.4.2, SVR will be measured from actual rather than planned end of treatment and the analysis windows should be amended accordingly. For these estimands, the date of last dose should be treated as the reference date and the rules in Table 4 should be used to determine the endpoint of SVR.

Table 4 Supplementary Endpoint Analysis Visit Windows for Arm 1 and Arm 2

Analysis Set / Domain	Parameter	Reference Day	Analysis Window		Analysis Timepoint
			Beginning Timepoint	Ending Timepoint	
Efficacy	HBsAg and HBV DNA	Reference date	Reference date - 35	Reference date + 20	End of Actual treatment
Efficacy	HBsAg and HBV DNA	Reference date + 56	Reference date + 21	Reference date + 76	Post treatment Week 8
Efficacy	HBsAg and HBV DNA	Reference date + 126	Reference date + 77	Reference date + 132	Post treatment Week 18
Efficacy	HBsAg and HBV DNA	Reference date + 168	Reference date + 133	Reference date + 188	Post treatment Week 24

If all analysis windows have non-missing response information, a participant's response (Responder or Non-responder) is determined as follows:

1. If rescue medication was used during on-treatment or off-treatment period, then the participant is a non-responder.
2. If HBsAg <LLOQ and HBV DNA <LLOQ in each of the analysis windows, then the participant is a responder, otherwise the participant is non-responder.
3. A result of TND is considered as <LLOQ.

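### The SVR rescue rules have no end date, so only Arm 2 can fail the 24-week endpoint on rescue first used after off-treatment Week 24

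*SAP*

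**What the plan says.** Two SAP rules for the final analysis turn rescue use into SVR failure.

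- SAP 4.2.2.1, responder rule 1: "If rescue medication was used during on-treatment or off-treatment period, then the participant is a non-responder".
- SAP 4.2.2.2, near its end: a participant with any HBsAg or HBV DNA at or above LLOQ, or with "rescue medication usage at or after the planned end of sequential treatment (EoT), the subject will be classified as an SVR non-responder".

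Neither rule states when counting stops. The off-treatment period differs by arm. The protocol synopsis has "Arm 1: 24 weeks GSK3228836 + 24 weeks PegIFN + 24 weeks off-treatment"; for Arm 2, protocol 4.1 says "Participants will be followed up for an additional 36 weeks (off-treatment phase) once PegIFN treatment is complete".

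Other passages set a Week 24 horizon for the two markers. Protocol 9.4.2: "HBsAg and HBV DNA from the week of end-of-treatment to Off-Treatment Week 24 will be used to assess the primary endpoint for each arm". SAP 4.2 takes data from the end-of-treatment window "to the off-treatment Week 24 analysis window will be used to analyse the primary endpoint for each arm". SAP 4.2.2.1 says that windowed results determine SVR, and its rule 2 requires both markers below LLOQ "in each of the analysis windows, then the participant is a responder, otherwise the participant is non-responder". The estimand variable in SAP 4.2.1 is response "for 24 weeks after the planned end of sequential treatment, without the use of rescue medication".

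**The concern.** SVR is meant to be a 24-week endpoint in both arms. A failure rule that runs over the whole off-treatment period gives Arm 2 twelve further weeks in which to fail. Take an Arm 2 participant who is below LLOQ on both markers in every window to off-treatment Week 24 and first uses rescue around Week 30. Under the rescue rules this is a non-responder. The same course in Arm 1 is never observed, because follow-up there ends at off-treatment Week 24 (study Week 72). The primary analysis runs after the last Week 72 visit, so the late Arm 2 data will be in the database.

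The HBsAg/HBV DNA part of the SAP 4.2.2.2 sentence has the same open end, but there it contradicts other text, so a programmer could derive the endpoint in two ways.

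The result enters the Arm 2 SVR rate and the two between-arm probabilities in SAP 4.3.1.3, Pr(Arm 1 − Arm 2 > 0) and Pr(Arm 2 − Arm 1 > −0.05), which are presented to help choose the regimen. It would also move late events out of the separate Arm 2 durability objective (SAP 4.3.1.2) and into the primary endpoint.

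**Working it through.** **1. The plan's own figures.** Inputs (protocol 9.2, SAP 5): n = 50 per arm, prior Beta(0.5, 0.5), criterion posterior probability > 65%. The cut-off is the smallest y with P(p > t | Beta(y + 0.5, 50 − y + 0.5)) > 0.65. This gives y = 12 for t = 20% and y = 17 for t = 30%. Then P(X ≥ 12 | 50, 0.30) = 86.1% and P(X ≥ 17 | 50, 0.40) = 84.4%, against about 86% and 84% stated. They reproduce. They do not test the point; they are the base for sizing it.

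**2. Time at risk** (days from SAP Tables 2, 3 and 19).

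| | Arm 1 | Arm 2 |
|---|---|---|
| EoT target day | 330 | 246 |
| Week 24 target day | 498 | 414 |
| Week 24 window ends | 518 | 434 |
| Window end minus EoT target | 188 | 188 |
| Last scheduled visit | 498 | 498 |
| Last visit minus EoT target | 168 (24 weeks) | 252 (36 weeks) |

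The tabulated windows are symmetric. Without an end date, Arm 2 is exposed for a further 498 − 414 = 84 days past its Week 24 target, or 498 − 434 = 64 days past its window. The off-treatment Week 30 and 36 visits (days 456 and 498) lie in no primary window.

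**3. Which passages set an end date.**

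| Passage | HBsAg / HBV DNA | Rescue |
|---|---|---|
| Protocol 9.4.2; SAP 4.2 | Week 24 | not addressed as a cut-off |
| SAP 4.2.2.1, windowing, rule 2, Table 3 | Week 24 window | not covered |
| SAP 4.2.2.1, rule 1 | – | whole off-treatment period |
| SAP 4.2.2.2 | open-ended | open-ended |
| SAP 4.2.1 estimand | 24 weeks | 24 weeks only by implication |
| SAP 4.7.4, interim only | – | up to the endpoint assessment |

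For rescue, no rule in the final analysis states a limit. For the markers, one sentence conflicts with the rest.

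**4. Sensitivity per participant.** Assumption: 14/50 responders in each arm at Week 24, independent Beta(y + 0.5, 50 − y + 0.5) posteriors, 2,000,000 draws. This is not the SAP's logistic model.

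| Arm 2 participants reclassified | Arm 2 count | Pr(Arm 2 − Arm 1 > −0.05) | Pr(Arm 1 − Arm 2 > 0) |
|---|---|---|---|
| 0 | 14 | 0.714 | 0.500 |
| 1 | 13 | 0.635 | 0.589 |
| 2 | 12 | 0.549 | 0.676 |
| 3 | 11 | 0.458 | 0.756 |

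Successive falls in the first probability are 0.079, 0.086 and 0.091. In a single arm, moving from 17/50 to 16/50 takes P(rate > 30%) from 0.735 to 0.628, across the 65% line.

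**5. Range for the unknown rate.** Let r be the share of Arm 2's Week 24 responders with a late event that is counted. The documents give no value; 0 to 20% is assumed. The rate becomes q = p(1 − r).

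| r | P(X ≥ 12), p = 0.30 | P(X ≥ 17), p = 0.40 |
|---|---|---|
| 0 | 86% | 84% |
| 5% | 80% | 77% |
| 10% | 73% | 67% |
| 20% | 55% | 43% |

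Arm 1 is unchanged throughout.

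**The case against.** The best defence is that the endpoint is already bounded. SVR is determined from windowed results, Table 3 ends at day 434, and the later visits supply no windowed result. The SAP 4.2.2.2 sentence sits in a missing-data section and ends by ruling out imputation, so it reads naturally as a precedence rule: an observed failure is not overwritten by imputation for a disruptive event. SAP 4.3.1.3 describes the arm comparison as running up to 24 weeks off treatment. Rescue excludes the background NA (SAP 2), which continues throughout, so first rescue after a clean Week 24 may never occur.

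For the two markers this largely stands. A reader might infer that Arm 2's SVR becomes a 36-week rate, perhaps helped by the phrase in SAP 2 about response lasting six months or more. The documents do not support that: protocol 9.4.2, SAP 4.2, the windowing rule, rule 2 and Table 3 all stop at Week 24, and one loosely worded sentence does not override them.

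For rescue the defence falls short. Rescue use is not a windowed laboratory result, so the windows do not limit it. Rule 1 names the whole off-treatment period and comes before rule 2. The estimand and comparison wording imply a 24-week limit, but neither rule that classifies participants applies it. The interim section does, which shows that the limit could have been written.

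**Conclusion.** The point holds for rescue medication: as written, two final-analysis rules can fail an Arm 2 participant on an event after off-treatment Week 24, with no equivalent exposure in Arm 1. For HBsAg and HBV DNA it holds only as an internal conflict in SAP 4.2.2.2, which the remaining text resolves in favour of Week 24.

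Any effect runs one way, against the 12-week regimen. Its size cannot be derived from the documents and may be zero. The per-participant falls of about 0.08 to 0.09 rest on the assumed 14/50 in each arm and on independent Beta posteriors; they show sensitivity and do not predict an effect. The 0 to 20% range is also an assumption and covers late events by any route, so it should not be read as an estimate for rescue alone.

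**What to change.** Apply one Week 24 limit in both SAP 4.2.2.1 rule 1 and SAP 4.2.2.2:

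- HBsAg or HBV DNA at or above LLOQ counts only up to the off-treatment Week 24 window in Tables 2 and 3.
- Rescue counts only up to the participant's off-treatment Week 24 assessment or, if that is missing, its target day (498 in Arm 1, 414 in Arm 2). Using the assessment rather than the window end avoids leaving Arm 2 exposed for a further 434 − 414 = 20 days while Arm 1 has finished.
- For the estimands measured from actual end of treatment, use the matching Table 4 limits: the post-treatment Week 24 window for the markers, and for rescue the assessment in it or, if missing, reference date + 168.
- Report later Arm 2 rebound or rescue only under the durability objective in SAP 4.3.1.2.

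SAP 4.7.4 needs no change for rescue, since it already stops at the endpoint assessment. A small residual remains for the markers: unscheduled Arm 2 tests between the Week 24 visit and day 434 still fall in the window. The cost is a few sentences and a date limit in the derivation. No new data are needed, and the model and sample size stay as they are.
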